**Background and overall aim**

Osteoporosis is a systemic skeletal disease affecting more than 75 million people in Europe, Japan and USA [1]. It is defined as a condition of decreased bone mineral density (BMD) and changes in the microarchitecture of the bone tissue. This leads to decreased bone strength and an increased risk of fractures, primarily in the hip, spine and wrist.

The most common form of osteoporosis is called primary osteoporosis and affects mainly elderly patients. It is three times more common in women than in men and this can be explained by the lower peak bone mass in women as well as by the hormonal changes that occur at the menopause. Furthermore, women live longer than men and thus have larger reductions in bone mass. It has been estimated that 30% of all postmenopausal women have osteoporosis [2].

It is still not clear whether systemic osteoporosis also results in osteoporosis of the jaws and systemic osteoporosis was for a long time considered a contraindication for treatment with dental implants. This view has changed over the years but there are still many dentists who consider not to treat osteoporotic patients with dental implants due to fear of unsuccessful outcomes.

The overall aim of the study is to compare treatment with dental implants (the Astra Tech OsseoSpeed™ implant) in the maxilla of postmenopausal women with and without systemic osteoporosis/osteopenia.

**Study objectives**

*Primary objective*

The primary objective is to compare marginal bone level (MBL) alterations following treatment with the OsseoSpeed™ implant in the maxilla of post-menopausal women with and without systemic osteoporosis/osteopenia. Marginal bone level alterations will be evaluated by radiological assessments and MBL values at prosthetic insertion will be used as baseline.

*Secondary objectives*

The secondary objectives of the study are to evaluate (i.e. compare between the groups):

- Implant survival
- Implant stability, by using resonance frequency analysis (RFA)
- Condition of periimplant mucosa by assessment of Bleeding on Probing (BoP), Probing Pocket Depth (PPD) and Attachment Level (AL)
- Safety by recording of adverse events (AEs) and adverse device effects (ADEs)
- Patient reported outcomes by the Oral Health Impact Profile (OHIP)

*Additional objective*

The additional objective of the study is to evaluate the correlation between BMD in the skeleton (hip/spine) with BMD in the maxilla.

## Study design

This will be an open, prospective, non-randomized, controlled parallel-group multicenter study to document the outcome of treatment with the OsseoSpeed™ implant in the maxilla of postmenopausal women with systemic osteoporosis/osteopenia. Two groups will be included in the study: *Group A (osteoporosis/osteopenia)* consisting of postmenopausal women with low BMD values (T-score  $\leq -2$ ) and *Group B (control)* consisting of postmenopausal women with normal BMD values (T-score  $\geq -1$ ). Each subject will receive 2-8 splinted implants in the maxilla and two-stage surgery will be used.

A total of 104 subjects fulfilling all of the inclusion criteria and none of the exclusion criteria will be included. Fifty-two subjects will be included in group A (osteoporosis/osteopenia group) and fifty-two in group B (control). Four centers will be involved in the study, each center treating 13 osteoporotic/osteopenic subjects and 13 control subjects.

The study will be a five-year follow-up study comprising of 13 visits:

### *Visit 1 – Screening*

The screening visit will include collection of demographic data as well as clinical and radiographic assessments. Subjects fulfilling all inclusion criteria and none of the exclusion criteria after the screening visit will be scheduled for BMD measurements in the hip and the spine, using dual energy X-ray absorptiometry (DXA). Subjects fulfilling all inclusion criteria for either Group A or Group B and none of the exclusion criteria will be scheduled for Visit 2.

### *Visit 2 - Pre-surgical planning*

Subjects will undergo a dental quantitative computed tomography (CT) examination in order to determine the BMD at the planned implant sites. The treatment plan will be discussed with the subject.

### *Visit 3 – Surgery I (Implant placement)*

The surgical procedure will be performed under local anesthesia. After a crestal incision, 2-8 implants will be placed in the maxilla. Cover screws will then be inserted into the implants and the mucoperiosteal flaps sutured back for a tight seal.

### *Visit 4 - Post-operative check-up*

One week after implant placement the subjects will return for control of the implants and the healing process.

### *Visit 5 – Surgery II (Abutment placement)*

At 12 weeks after implant placement, a second surgical procedure will be performed. A small mucosal incision will be made under local anesthesia, the cover screws will be removed and healing abutments will be connected to the implants.

### *Visit 6 – Impression*

After 1 week of soft tissue healing, impressions will be taken for fabrication of the screw-retained permanent restoration(s).

### *Visit 7 – Permanent restoration (PR)*

The screw-retained permanent restoration will be delivered between 4 and 8 weeks after the impression visit.

### *Visits 8-13 – Follow-up (PR+6 to 60 months)*

The subject will return for follow-up visits at 6, 12, 24, 36, 48 and 60 months after permanent restoration.

## Rationale for study design

An open study design has been chosen primarily for ethical reasons since the subjects with osteoporosis and osteopenia will be followed-up and treated by their GP:s and therefore will be informed about their diagnosis. Furthermore, the treating dentists (the Investigators) need to be informed about the subjects' medication etc. to be able to offer proper therapy. However, the primary variable of the study, i.e. marginal bone alterations, will be assessed by blinded independent radiologists.

The reason for including both osteoporotic and osteopenic subjects in Group A is the fact that it would be difficult to find a sufficient number of subjects with osteoporosis (T-score  $\leq -2.5$ ) in need of 2-8 implants in the maxilla. By choosing a T-score  $\leq -2$  as an inclusion criterion the subjects will still have a reduced, and for the study relevant, BMD and the possibilities of recruiting the required number of subjects will be markedly increased.

A control group (Group B) was included to assure a relevant comparison of the results from Group A (osteoporosis/osteopenia) with non-osteoporotic women treated in the same way.

In order not to jeopardize the treatment results for the subjects, in case the systemic osteoporosis/osteopenia actually has an effect on the implant treatment success, a two-stage surgery protocol was chosen.

The subjects will be followed-up for 5 years after prosthetic restoration. The largest marginal bone alterations are normally seen within the first year after implant placement. By studying the subjects for more than 5 years after implant placement, long-term alterations will be revealed and the possibility to detect a difference between the groups will increase.

## Risk/benefit assessment

In this study subjects with osteoporosis will be treated with dental implants. This patient group has previously often been excluded from implant therapy but since previous studies have shown successful results in osteoporotic subjects after implant treatment [3-6] we expect good results in both study groups.

The osteoporotic/osteopenic group will presumably consist both of women with known osteoporosis and women with previously unknown osteoporosis. The osteoporotic subjects will be treated according to routine health care. This means that some of the patients may have been treated with bisphosphonates prior to implant treatment. There is recent data available, describing cases of osteonecrosis of the jaws after dental surgery in patients concomitantly treated with bisphosphonates [7]. This complication seems to be rare and there is not enough data existing to prove a causal link between the use of oral bisphosphonates and osteonecrosis of the jaws. However, we can not ignore a small but possible risk for subjects on bisphosphonates to develop osteonecrosis of the jaws. In order to minimize this risk, we have chosen not to include patients who have been taking oral bisphosphonates for 3 years or more. The subjects will also be carefully informed about the risks of osteonecrosis of the jaws before entering the study. This is in accordance with a position paper published by the American Association of Oral and Maxillofacial Surgeons [8]. In summary, we assess the risk of entering the study as low. The benefit of entering, on the other hand, would be for a patient to have an unknown osteoporosis diagnosed and treated. The risk benefit analysis therefore must be considered as favorable for entering the study.

N.B. Oral bisphosphonates is not considered a contraindication for implant treatment.

## Study population

### *Inclusion criteria*

For inclusion in the study subjects must fulfill all of the following criteria:

1. Provision of informed consent
2. Postmenopausal women aged 60 years and over
3. In need of 2-8 implants in maxilla
4. A history of edentulism in the area of implant treatment of at least 6 months.
5. A BMD value suitable either for group A **or** group B:

**Group A (Osteoporosis/osteopenia):** BMD at least 2 standard deviations below mean peak bone density of young adults for the spine and total hip (T-score $\leq$ -2SD). Absolute values (g/cm^2) will be used.

**Group B (Control):** BMD not more than 1 standard deviation below mean peak bone density of young adults for the spine and total hip (T-score $\geq$ -1SD). Absolute values (g/cm^2) will be used.

### *Exclusion criteria*

Any of the following is regarded as a criterion for exclusion from the study:

1. Unlikely to be able to comply with study procedures, as judged by the investigator.
2. Untreated, uncontrolled caries and/or periodontal disease
3. Known or suspected current malignancy
4. History of chemotherapy within 5 years prior to surgery
5. History of radiation in the head and neck region
6. History of other metabolic bone diseases, e.g. Paget's disease, hyperparathyroidism, fibrous dysplasia or osteomalacia
7. A medical history that makes implant insertion unfavorable
8. Need for systemic corticosteroids
9. Previous or current use of intravenous bisphosphonates (esp. zoledronic acid)
10. Use of oral bisphosphonates for  $\geq$  3 years
11. History of bone grafting and/or sinus lift in the planned implant area
12. Current need for bone grafting and/or sinus lift in the planned implant area
13. Present alcohol and/or drug abuse
14. Involvement in the planning and conduct of the study (applies to both Astra Tech AB staff or staff at the study site)
15. Previous enrolment in the present study.
16. Participation in a clinical study during the last 6 months.

## Study products

The OsseoSpeed™ implant is a screw-shaped and self-tapping implant with diameters of 3.5S, 4.0S, 4.5, 5.0 and 5.0S mm. Implants are available in lengths of 8, 9, 11, 13, 15, 17 and 19 mm. MicroThreads™ characterize the coronal aspect of the OsseoSpeed™ implant.

The OsseoSpeed™ surface is developed by a TiO2-blasting procedure creating a rough surface, which is then modified through a cleaning process in diluted hydrofluoric acid.

## Statistical methods

The primary objective is to test the hypothesis that the alteration in MBL from prosthetic restoration to the 5-year follow-up visit is equal (i.e. a two-sided hypothesis) in patients in group A and in group B. The hypothesis will be tested by means of the Wilcoxon rank sum test. A p-value less than 5% at the 5-year follow-up visit will be considered statistically significant. In addition, the time to certain degrees of alterations will be estimated by means of Kaplan-Meier plots and the hypothesis that the time is equal in group A and B will be tested by means of the log-rank test.

The secondary objectives are to test:

- The hypothesis that the survival rate is equal among implants on patients in group A and B by means of the Fisher's exact test (i.e. implant level). Furthermore, the time to implant loss will be estimated by means of Kaplan-Meier plots and the hypothesis that the time is equal in group A and B will be tested by means of the log-rank test.
- The hypothesis that the proportion of survived implants is equal in patients in group A and B by means of the Wilcoxon rank sum test (i.e. patient level).
- The hypothesis that the condition of peri-implant mucosa is equal in patients in group A and B by means of the Wilcoxon rank sum test.

The evaluation of the correlation between skeletal and maxillary BMD will be estimated by means of the Spearman's rank correlation coefficient on patient level.

All safety variables will be summarized by means of descriptive statistics. No hypotheses will be tested.

The hypothesis that the OHIP is equal in patients in group A and B will be tested by means of the Wilcoxon rank sum test

All hypotheses will be tested at all visits. P-values will be calculated but not called statistically significant except for the primary objective at the final visit.

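### Does the MBL analysis need a written rule for implants that are lost before the 5-year visit?

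*Combined protocol and SAP*

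**What the plan says.** Under Study design, "Each subject will receive 2-8 splinted implants in the maxilla". Under Study objectives, "MBL values at prosthetic insertion will be used as baseline". The Statistical methods section makes the primary comparison a two-sided Wilcoxon rank sum test, at 5%, of the hypothesis that the "alteration in MBL from prosthetic restoration to the 5-year follow-up visit is equal" in the two groups. It adds that "the time to certain degrees of alterations will be estimated by means of Kaplan-Meier plots", with a log-rank test.

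Implant loss is a secondary objective with three comparisons of its own: Fisher's exact test at implant level, a log-rank test of time to loss, and a patient-level Wilcoxon test of the hypothesis that "the proportion of survived implants is equal in patients in group A and B".

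On timing and error control, "All hypotheses will be tested at all visits", and "P-values will be calculated but not called statistically significant except for the primary objective at the final visit". The Rationale section says that "An open study design has been chosen primarily for ethical reasons", but also that MBL is read by blinded independent radiologists.

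Nothing in the available text says what a lost implant contributes to the patient's MBL change, or whether a loss is an event or a censoring in the MBL Kaplan-Meier analysis.

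**The concern.** Implants are placed at Visit 3 and restored 12 + 1 + 4 to 8 = 17 to 21 weeks later. A loss in that window leaves no baseline MBL, and a later loss leaves no 5-year MBL. The plan foresees losses, since it gives them their own hypotheses. An analyst must therefore do something with them: drop the implant from the patient's value, drop the patient, carry a value forward, or assign a worst value.

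The rule feeds the one objective for which significance may be claimed. Group membership is known, and group comparisons are planned at every visit. The text does not say when those comparisons are run. If they are run as visits complete, a rule settled late could be settled with the group results in view. Blinded reading protects the measurements but not that choice. What would be at stake is some power and, if the rule were picked for its p-value, the 5% level.

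**Working it through.** **The plan's own figure.** 4 centres × 13 = 52 per group, and 2 × 52 = 104. This is consistent. The available text gives no effect size, SD, correlation, dropout or loss rate, so everything below rests on assumptions: number of implants uniform on 2 to 8, equal unrelated loss of 3% or 5% of implants, within-patient correlation 0.5 (range 0.3-0.7), and an effect of 0.5 SD, with the SD at implant level.

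**Patients affected.** P(at least one loss) = 1 − (1 − p)^m, averaged over m = 2,…,8.
- p = 0.03: the mean of 0.97^m is 0.860, so 104 × 0.140 = 14.5 patients.
- p = 0.05: the mean of 0.95^m is 0.778, so 104 × 0.222 = 23.1 patients.

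**Power with no losses.** The variance of a patient mean, in implant-level units, is 0.5 + 0.5/m. The mean of 1/m is 0.245, giving 0.623 and an SD of 0.789. The effect in patient-level SD is 0.5 / 0.789 = 0.634. With the Wilcoxon efficiency of 0.955 under normality, z = 0.634 × √(52/2) × √0.955 − 1.96 = 1.20, so power is about 88%.

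The unit matters. If 0.5 SD were at patient level, z = 0.5 × 5.10 × 0.977 − 1.96 = 0.53, so power is about 70%.

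**Power leaving out every patient with a loss.** Numbers per group fall to (104 − 14.5)/2 = 44.7 and (104 − 23.1)/2 = 40.4. The same formula gives z = 0.97 and 0.82, so power is about 83% and 79-80%.

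**Simulation on the same assumptions** (2,500 replicates per power setting, correlation 0.5):

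| Rule for a lost implant | Power, 3% loss | Power, 5% loss |
|---|---|---|
| Mean of evaluable implants | 88% | 87% |
| Last value carried forward | 88% | 87% |
| Implant-level worst rank | 86% | 84% |
| Patient with any loss left out | 83% | 78% |
| Patient with any loss ranked worst | 62% | 46% |

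Over correlations 0.3-0.7, leaving patients out costs 3-10 points against the evaluable mean, and the two verdicts differ in 5-16% of trials. If losses cluster within patients (latent correlation 0.5), about 11 and 17 patients are affected instead of 15 and 23, and the cost falls to about 4 and 5 points.

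**Type I error** (4,000 replicates per setting). Each rule alone rejects 4-6%. Taking the better p-value of the evaluable mean and the left-out rule rejects 6-8%. Taking the best of four rules rejects 7-9%, and 9-12% if ranking any loss worst is added.

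**MBL log-rank** (patient level assumed, 30% vs 10% reaching the threshold, 3% / 5% loss). Power is 73% / 74% with the lost implant dropped, 68% / 67% with the patient censored at first loss, and 45% / 35% with loss counted as an event.

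**Would a difference in loss be seen elsewhere?** At 8% vs 2% unrelated loss, the planned patient-level Wilcoxon has 87% power and Fisher's test 89%. With clustered losses these become 67-75% and 80-84%. The Fisher figures are then too high, because that test ignores clustering.

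**The case for a change.** The strongest case for a change is that the rule can decide what a significant primary result means. In a separate simulation with clustered loss of 10% vs 2% and no MBL difference among retained implants, the primary test rejects 5% of the time if lost implants are dropped and 54% if any patient with a loss ranks worst. A sentence or two would cost little, and the study is open.

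Much of this is true, but it does not show a defect. Ranking any loss worst turns the endpoint into a composite of bone change and failure. The plan does not ask that question: it tests MBL alteration, and it tests loss on its own. Counting loss as an event in the MBL Kaplan-Meier analysis does the same. Nothing in the text points to either rule, or to discarding every patient who loses one implant out of several. The inflated error rates require choosing a rule for its p-value.

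Two points stand. An MBL analysis of evaluable implants describes surviving implants, so if loss follows bone loss the observed difference is somewhat reduced, and it has to be read with the survival results. Those survival p-values are not to be called significant. Both follow from the plan's choice of endpoints, and a written rule for lost implants would not remove them.

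Nor would the proposed wording be neutral. Specifying a patient mean fixes how 2-8 implants are combined, and a rule keeping the patient at risk assumes a patient-level Kaplan-Meier analysis. The text states neither. The log-rank also sits in the primary-objective paragraph, so whether its p-value could be called significant is itself open to reading.

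**Conclusion.** The text is silent on lost implants in the MBL analyses, but this is missing detail rather than an error. An analyst following the section would use the implants measured at both restoration and 5 years. That test keeps its level, and loss is covered by three planned comparisons.

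Among the rules that keep the patient and treat loss implant by implant, power ranges from 84% to 88%. Leaving out affected patients costs 3-10 points, and less if losses cluster. Choosing between that rule and the evaluable mean afterwards would bring 5% to about 6-8%. The larger gaps need rules that nothing in the plan suggests. All of these sizes rest on assumed loss rates, correlations and an effect of 0.5 implant-level SD, since the documents give none.

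The sponsor may record the convention before group results are seen, including the case of a patient who loses every implant, but the plan does not depend on it. The statistical section is short and a fuller document may hold the rule. No change is called for.

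### The only confirmatory test is unadjusted in a non-randomised comparison not matched on age, and no supporting analysis is planned that could tell bone status from age

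*Combined protocol and SAP*

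**What the plan says.** Study design describes an "open, prospective, non-randomized, controlled parallel-group multicenter study". Its one balancing feature is by centre: "each center treating 13 osteoporotic/osteopenic subjects and 13 control subjects".

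Under Inclusion criteria, Group A requires "BMD at least 2 standard deviations below mean peak bone density of young adults for the spine and total hip". Group B may lie no more than 1 SD below the same young-adult reference. Age enters only through "Postmenopausal women aged 60 years and over", with no upper limit, matching or strata.

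Background and overall aim states: "The most common form of osteoporosis is called primary osteoporosis and affects mainly elderly patients". It sets the purpose in these words: "The overall aim of the study is to compare treatment with dental implants", in women with and without the condition.

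Under Statistical methods, the primary hypothesis is equal MBL change in the two groups from prosthetic restoration to 5 years, at a two-sided 5% level: "The hypothesis will be tested by means of the Wilcoxon rank sum test". A log-rank test on time to given degrees of change is added, also without covariates. On all other results: "P-values will be calculated but not called statistically significant except for the primary objective at the final visit". No adjusted model or sensitivity analysis is named. Demographic data are collected at Visit 1 but are assigned to no comparison.

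**The concern.** A T-score measured against young adults falls as bone is lost with age, and the protocol itself ties primary osteoporosis to old age. Group A is therefore plausibly older than Group B, even with everyone at least 60. If age is also related to MBL change, the planned test responds to the sum of the two influences. It could report a difference that is due to age alone, or miss a real one if age works the other way. A larger sample would not help, because this is bias and not noise.

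The control group was included, according to Rationale for study design, so that Group A can be set against comparable non-osteoporotic women. Only the 5-year primary p-value may be called significant. If it is hard to interpret, nothing else in the plan is designed to clarify it. Blinded reading of the radiographs deals with assessment bias, not with this.

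**Working it through.** **1. The plan's own figure.** 4 centres × (13 + 13) = 104, so 4 × 13 = 52 per group. This reproduces. No power, effect size or SD is stated, so there is nothing further to reproduce.

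**2. Inputs.** From the documents: 52 per group, four centres with 13 + 13, two-sided 5%, Wilcoxon test. Assumed, because the documents give no values: a normal outcome; Group A older by g = 0.25, 0.5 or 0.8 within-group SD; a within-group correlation between age and MBL change of r = 0.1 to 0.4.

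**3. Formula.** With no group effect at equal age, the group means differ by g × r outcome SDs. The Wilcoxon rejection rate is approximately

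1 − Φ(1.96 − δ) + Φ(−1.96 − δ), with δ = (g × r) / √(2/52) × √(3/π).

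Here √(2/52) = 0.196 and √(3/π) = 0.977. For g = 0.5 and r = 0.3, g × r = 0.15, δ ≈ 0.75, and the rate is about 11.6%.

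**4. Simulation, no group effect at equal age** (20,000 replicates per cell). Wilcoxon rejections, %:

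| Age gap (SD) | r = 0.1 | 0.2 | 0.3 | 0.4 |
|---|---|---|---|---|
| 0.25 | 5.1 | 5.6 | 6.6 | 7.7 |
| 0.5 | 5.5 | 7.7 | 11.3 | 16.5 |
| 0.8 | 6.9 | 12.2 | 22.0 | 34.9 |

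The cell for g = 0.5 and r = 0.3 gives 11.3%, in line with the formula. If g or r is zero, the rate stays near 5%. The product g × r drives the result: about 5.6% at 0.05, 7.7% at 0.10, 11% at 0.15 and 16.5% at 0.20. A rank model with group, ranked age and centre stays at 4.9–5.2%, but by construction, since age is the only confounder simulated.

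**5. Masking.** True difference 0.55 SD with age acting the opposite way; Wilcoxon power is 77% without an age influence. Power, %:

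| Age gap (SD) | Wilcoxon, r = 0.1 / 0.2 / 0.3 / 0.4 | Adjusted model |
|---|---|---|
| 0.25 | 74 / 69 / 65 / 60 | 77–82 |
| 0.5 | 70 / 60 / 50 / 41 | 75–80 |
| 0.8 | 64 / 49 / 33 / 20 | 71–75 |

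**6. What reading the two analyses together would reveal.** At a gap of 0.8 SD and r = 0.2/0.3/0.4, with no true difference, only the Wilcoxon is significant in 9.5/19.2/32.0% of trials. In the masking case at the same gap and r, only the adjusted model is significant in 23/40/55%.

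**7. Losses.** With an assumed 40 per group, the Wilcoxon rejects in 5.2–13.5% (0.5 SD) or 6.0–28.3% (0.8 SD) under no group effect.

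**8. A second factor.** Suppose 40% of Group A and none of Group B had used oral bisphosphonates, with an effect of 0.4 or 0.8 SD, an age gap of 0.5 SD and no age effect. The age-and-centre model still rejects in 12% or 30%, against 5.1% or 5.5% with use in the model.

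**The case against.** The strongest reply is that the study asks about the groups as found. The objectives compare women with and without the condition, the stated motive is dentists' reluctance to treat such patients, and no section claims an age-independent or causal effect. On that reading the Wilcoxon answers the question posed. This stands, and it is why neither the hypothesis nor the test needs replacing. A reader might infer that the test is invalid; the documents do not support that.

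A reader might also infer that age and bone status cannot be separated in this study at all. That goes too far. Age should be among the Visit 1 demographic data, so adjustment is feasible where the age ranges overlap. The limitation belongs to the analysis as written.

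A third tempting inference is that the primary result will be biased by age. The age gap is only suggested by a general statement about osteoporosis, and limiting both groups to women of 60 or more is already a partial control. Nothing in the text links age to MBL change. The rates of 20% and above need a 0.8 SD gap and r of at least 0.3, which nothing in the documents establishes.

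Two further points stand. Age adjustment does not deal with oral bisphosphonates: Risk/benefit assessment foresees prior use in osteoporotic subjects, and the exclusion criteria bar only use of 3 years or more. And since the statistical section is short, a baseline table may be intended but unstated.

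What remains is that, followed exactly, the plan leaves any age difference unexamined. Centre is not part of the problem if the 13 + 13 quotas are met.

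**Conclusion.** The concern holds as a limit on interpretation. The Wilcoxon is a valid test of whether the groups as found differ, but no planned analysis would show whether a difference, or none, reflects osteoporosis/osteopenia or age. The consequence ranges from nil, if either link is absent, to roughly a third of null trials rejecting at the extreme of the assumed grid. It is small when the age gap in SDs times the correlation is below about 0.10. Both quantities are assumptions. The gap in the plan is certain and its practical size is not, so this is a cheap improvement and not a defect that undermines the primary test.

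**What to change.** In Statistical methods, keep the hypothesis and the Wilcoxon test, and add:

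> A pre-specified supporting analysis will fit the ranks of the 5-year MBL change (one value per patient) on group, age at screening (ranked) and centre. Its group estimate and p-value will be reported beside the Wilcoxon result and the two interpreted together in both directions: a difference that fades after adjustment may reflect age, and one that appears only after adjustment may have been masked by age. The two need not both be significant. Age and other screening variables will be tabulated by group.

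Add one sensitivity model that also includes prior oral bisphosphonate use, where recorded, and state that residual confounding remains. Label that model descriptive, because use is closely tied to group: with 40% use in Group A, no effect of use and a 0.5 SD age gap, power drops from 74% to 62%.

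Requiring both tests to be significant would not help. In the masking case at a 0.8 SD gap it gives 61/49/33/20% power for r = 0.1 to 0.4, no better than the Wilcoxon alone. Making the adjusted model primary is an option for the sponsor, not a requirement.

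**Cost.** A few lines of SAP text and code; the Wilcoxon test itself loses nothing. The adjusted estimate is less precise if ages differ but age is irrelevant. Adjusting for age inflates the variance of the group contrast by about 1 + g²/4, which is 1.06 at a gap of 0.5 SD and 1.16 at 0.8 SD. For an assumed true difference of 0.55 SD, power is then about 75% or 71%, against 77%. With no age gap and no centre effect the loss is negligible (77.1% to 76.9%). If centres differ (assumed SD 0.5, no age gap) the model gains power, from 71% to 77%. Specifying it now matters, because an adjustment chosen after seeing open-label data would carry less weight.

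### The single confirmatory test pools four centres that the design balances at 13 + 13; stratifying it by centre is a cheap improvement that protects power, and protects type I error if the A:B mix comes to differ widely between centres

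*Combined protocol and SAP*

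**What the plan says.** The Study design section of the combined protocol and SAP describes a non-randomised study and builds centre into enrolment: "Four centers will be involved in the study, each center treating 13 osteoporotic/osteopenic subjects and 13 control subjects". The total follows from this: "A total of 104 subjects fulfilling all of the inclusion criteria and none of the exclusion criteria will be included".

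The Statistical methods section compares 5-year change in marginal bone level (MBL) between the groups. The null hypothesis is that it "is equal (i.e. a two-sided hypothesis) in patients in group A and in group B", and the method is given in one sentence: "The hypothesis will be tested by means of the Wilcoxon rank sum test". The threshold is also stated: "A p-value less than 5% at the 5-year follow-up visit will be considered statistically significant". No other result can be declared significant: "P-values will be calculated but not called statistically significant except for the primary objective at the final visit".

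Neither the primary test nor any other analysis in that section mentions centre as a stratum, a model term or a sensitivity analysis. The documents give no expected size of centre differences, and do not say what happens if a centre misses its quota.

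**The concern.** Group is a characteristic of the patient, so nothing is randomised within a centre. Only the 13 + 13 quota keeps centre from being mixed with bone status. Surgery and restoration are done locally, so MBL change could differ by centre through operator, restoration or patient mix. Blinded independent reading of the radiographs limits reader differences but not these.

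Ranking all the women together has two possible consequences:

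- **Balance kept.** Centre effects cancel in the comparison of A with B, but the null variance of the pooled test still counts the spread between centres as noise. The test is then conservative and loses some power.
- **Balance badly broken.** If the A:B ratio differs a lot between centres, real centre effects leak into the group comparison, and the one p-value that may be called significant can partly reflect centre.

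Ranking within centre deals with both, using information already held on every subject.

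**Working it through.** **Inputs from the documents.** Two-sided alpha 0.05 (Statistical methods); four centres, 13 + 13 each (Study design). The plan's totals reproduce: 4 × 13 = 52 per group and 4 × 26 = 104.

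**Inputs that had to be assumed.** The plan gives no power, effect size, SD, dropout rate or ICC. I took normal data with within-centre SD 1, and ICC from 0 to 0.30, where ICC is the between-centre share of the variance of MBL change. The between-centre SD is then τ = √(ICC/(1 − ICC)): 0.333 at ICC 0.10 and 0.5 at ICC 0.20. The shift is the one detectable with 80% nominal power: (1.960 + 0.842) × √(2/(52 × 0.955)) = 0.562 SD, where 0.955 is the Wilcoxon efficiency for normal data.

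**Step 1. Why the A:B ratio matters.** With aᵢ and bᵢ women from centre i in groups A and B (52 each in total), random centre effects add an error to the difference in means with SD τ × √Σ(aᵢ − bᵢ)² / 52. The ordinary standard error is √(2/52) = 0.196.

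- 13/13 in every centre: 0.
- Mild (A/B 15/11, 14/12, 12/14, 11/15): √(16 + 4 + 4 + 16)/52 = 0.122, times τ = 0.041 at ICC 0.10 and 0.061 at 0.20.
- Wide (A 20/16/10/6, B 8/12/15/17): √(144 + 16 + 25 + 121)/52 = 0.336, times τ = 0.112 at ICC 0.10 and 0.168 at 0.20.

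The mild error is small beside 0.196; the wide one is not.

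**Step 2. Quotas held.** Simulation of the pooled Wilcoxon against the van Elteren test (stratum weights 1/(Nᵢ + 1)), 40,000 runs per cell, Monte Carlo error about 0.1 point on alpha and 0.2 on power:

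| ICC | Pooled alpha | Pooled power | Stratified power | Pooled minus stratified (points) |
|---|---|---|---|---|
| 0 | 4.9% | 79.2% | 77.8% | +1.4 |
| 0.05 | 4.6% | 77.9% | 78.0% | −0.1 |
| 0.10 | 4.3% | 76.5% | 77.9% | −1.4 |
| 0.20 | 3.4% | 73.6% | 78.1% | −4.5 |
| 0.30 | 2.9% | 68.8% | 77.6% | −8.8 |

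Stratified alpha is 5.0-5.2% throughout. Separate runs with a shift of 0.57 SD agree: the loss is 1.2 to 1.6 points at ICC 0.10 and 4.5 at 0.20.

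**Step 3. Quotas not held, true null, random centre effects.** Pooled type I error:

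| Situation | ICC 0.10 | ICC 0.20 |
|---|---|---|
| Unequal centre sizes, 1:1 kept within each | 4.1% | 3.5% |
| Mild imbalance (as in step 1) | 4.5% | 4.3% |
| Moderate (A/B 18/8, 15/11, 11/15, 8/18) | 6.5% | 8.2% |
| Wide (A 20/16/10/6, B 8/12/15/17) | 7.1% | 9.8% |
| Extreme (A/B 22/4, 16/10, 10/16, 4/22) | 12.0% | 18.9% |

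The wide row comes from 20,000 runs; shorter runs gave 7.4-7.5% and 10.9%. The stratified test there has 5.2% and 4.8%, and stays at about 5% in the other imbalanced rows. If centre effects happen to line up with the imbalance, the mild case reaches only 5.4% and 5.9%, but the moderate case reaches 11.7% and 19.8%.

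**Step 4. Dropout from 13/13 enrolment.** Random loss, true null, 8,000 runs per cell, pooled type I error at ICC 0.10 and 0.20:

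- 20% in both groups: 4.6% and 3.8%.
- 30% in both groups: 4.2% and 3.9%.
- 35% in A and 15% in B: 4.3% and 4.2%.
- Loss varying from 5% to 40% by centre and group: 4.5% and 4.2%.

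None exceeds 5%.

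**Step 5. Cost of stratifying when centres do not differ.** Quotas held: 1.0 to 1.4 points. With 20% loss, 71.4% against 68.2%; with 30% loss, 62.8% against 60.1%. These two come from 3,000 runs, with a Monte Carlo error of about 0.8 point on each figure, so I read them as 2 to 3 points. Under the wide split: 6.2 points.

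**The case against.** The strongest reply is that the planned test is valid under the planned design. With 13 + 13 in each centre it errs on the safe side, and the power it gives up is trivial unless the ICC exceeds about 0.10. Nothing in the documents points to an ICC that large. The outcome is change from each woman's own value at restoration, which removes stable site differences in level, and the radiographs are read by blinded independent radiologists. Stratifying is also not free. All of this stands, and it is why the point is an improvement and not a defect that invalidates the test.

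Three stronger readings are tempting, and the documents do not support them.

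- **Any missed quota inflates false positives.** It does not. Unequal centre sizes with 1:1 kept, or mild imbalance, leave type I error at or below 5% with random centre effects, and at about 6% in the adverse alignment.
- **The plan itself expects quotas to fail.** The Rationale for study design says "it would be difficult to find a sufficient number of subjects with osteoporosis", but that clause concerns T-scores of −2.5 or lower. The next sentence gives the remedy already adopted: the cut-off of −2, which is expected to ease recruitment markedly. It is not evidence that quotas will be missed, still less that the A:B ratio will differ by centre.
- **Five years of attrition will mix group with centre.** Random loss, even at unequal rates, did not inflate the test. Only loss that shifts the A:B ratio substantially between centres would do so, and no passage predicts that.

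The objection leaves the asymmetry untouched. The quota is the sole safeguard against centre confounding, the analysis ignores it, and the documents do not say what happens if a centre falls short.

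**Conclusion.** The point holds as a cheap improvement. The omission of centre is plain in the text, and the direction of its effect is clear. Confidence in the size is only moderate, because the ICC, effect size, imbalance and normality are all assumed.

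- Quotas held: the pooled test is valid but conservative if centres differ. Power loss is nil up to ICC 0.05, 1 to 2 points at 0.10 and 4 to 5 at 0.20, with type I error about 4.3% at 0.10 and 3.5% at 0.20.
- Type I error inflates only when A:B ratios differ substantially between centres and centre effects are real: about 7% at ICC 0.10 and 10% at 0.20 for the wide split above.
- The documents do not show that either condition will occur, so the plan should not be described as having an inflated error rate.

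**What to change.** In Statistical methods, make the centre-stratified Wilcoxon (van Elteren) test the primary test of 5-year MBL change, and report the unstratified Wilcoxon as a sensitivity analysis. Suggested wording: *The primary comparison of MBL change at year 5 will use the Wilcoxon test stratified by centre (van Elteren, stratum weights 1/(Nᵢ + 1)); the unstratified test will be given as a sensitivity analysis.* Stratifying the log-rank tests in the same way is optional and was not evaluated here.

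The change is one sentence and needs no new data, since centre is known for every subject. It should be fixed before outcomes are seen, because a centre adjustment chosen afterwards would carry little weight. The price, if centres do not differ, is about 1 to 1.5 points of power with quotas held, 2 to 3 points with 20-30% dropout, and about 6 points under severe imbalance.
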